8.7 Analysis of Efficacy

Inflammatory lesion counts will be summarized at each evaluation from Baseline through Week 12. Absolute and percent change in lesion counts will be summarized at Weeks 2, 4, 8, and 12. IGA scores will be summarized from Baseline through Week 12 using descriptive statistics. The dichotomized IGA scores will be summarized at Weeks 2, 4, 8, and 12 using descriptive statistics.

All efficacy results will be presented in by-subject listings.

8.7.1 Primary Efficacy Analysis

The primary efficacy analysis will be presented on both the ITT and PP populations.

8.7.1.1 Lesion Counts

Tests of superiority for the absolute change from Baseline in inflammatory lesions will be based on either parametric or non-parametric methods consistent with the statistical assumptions required to support the analyses. Specifically, the tests of superiority will be based on an ANCOVA with factors of treatment and analysis center and the respective Baseline lesion count as a covariate or on ranked data submitted to an ANCOVA with factors of treatment and analysis center and the respective Baseline lesion count as a covariate. If the treatment-by-analysis center interaction effect is significant at an alpha less than 0.10, then the effect will be included in the model; otherwise it will be removed.

A skewness test, based on the methods presented by J.H. Zar [4], will be applied to the residuals resulting from an ANCOVA. A two-sided p-value for the skewness test significant at 0.01 will imply the use of the non-parametric method. If a parametric analysis is indicated, the results of the parametric analysis will be considered the primary analysis. Should a non-parametric analysis be indicated, the absolute or percent changes in inflammatory lesions will be rank transformed prior to submitting them to the ANCOVA. Results of the rank-transformed analyses then will be considered the primary analysis; however, results of the non-ranked transformed analyses will also be presented.

The following steps provide a brief synopsis of the process that will be followed.

1. Missing data will be imputed using multiple imputation. Refer to Section 8.1.5.1.
2. The pooling analysis will be conducted. Refer to Section 8.1.7.
 - a. The treatment-by-analysis center interaction p-values from both parametric and non-parametric (unranked and ranked) analyses will be presented, along with the skewness p-value calculated from the residuals from the unranked ANCOVA. The skewness p-value will determine which analysis results to report:
 - i. Skewness p-value > 0.01 : Report results based on the parametric (unranked) approach.
 - ii. Skewness p-value ≤ 0.01 : Report results based on the non-parametric (ranked) approach.
3. For the primary efficacy analysis
 - a. Results of both parametric and non-parametric (unranked and ranked) analyses will be presented. For each, data will be submitted to an ANCOVA with factors of treatment and analysis center and Baseline lesion count as a covariate (if the

treatment-by-analysis center interaction p-value is ≤ 0.10 , the interaction will also be included in the model). The residuals from the unranked analysis will be used to calculate the skewness p-value. The skewness p-value will determine which analysis results to report:

- i. Skewness p-value > 0.01 : Report results from the parametric (unranked) ANCOVA.
 - ii. Skewness p-value ≤ 0.01 : Report results from the non-parametric (ranked) ANCOVA.
4. If there was a significant treatment by analysis center interaction (as determined in step 1 – the pooling analysis), a sensitivity analysis will be performed as described in Section 8.1.7 to find the extreme analysis center(s). Then step 3 above will be repeated the extreme analysis center(s) removed, to confirm the treatment response.

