The consistency of treatment response will be investigated across the analysis centers subsequent to combining the data as described above. Statistical tests will be conducted to identify if there are extreme analysis centers that could affect the interpretation of common statistical and clinical conclusions. An analysis center by treatment interaction will be included in the primary analyses to test for parallel treatment effect at an alpha level of 0.10. Change from Baseline in inflammatory lesions will be analyzed with an ANCOVA (unranked or ranked) with factors of treatment group, analysis center, and treatment group by analysis center interaction, and the Baseline lesion count variable as a covariate. For the purpose of testing consistency of treatment response, the dichotomized IGA will be analyzed with a logistic regression with factors of treatment group, analysis center, and the interaction term of treatment group by analysis center. Further examination will follow for any variables that have a significant ANCOVA or logistic regression interaction term.

In the event that the ANCOVA or logistic regression interaction (referred to henceforth as the “appropriate test”) p-value is less than or equal to 0.10, a sensitivity analysis that excludes analysis centers with the extreme efficacy result will be performed to determine the robustness of the treatment effect. On the other hand, if all three analyses result in interaction terms with p-values greater than 0.10, then the conclusions from the pooled data will be considered to be free of the impact of extreme analysis centers.

The first step in conducting a sensitivity analysis is to identify the extreme analysis center or centers that contribute to the statistical significance of the appropriate test. The process involves submitting subsets of analysis centers to the appropriate test and observing the appropriate test p-value for the subset. Subsets with p-values greater than 0.10 for the appropriate test are considered homogeneous.

The search for an extreme analysis center begins by analyzing all subsets that can be created by excluding one analysis center. If one or more of the subsets result in an appropriate test p-value greater than or equal to 0.10, then the analysis center excluded from the subset with the largest p-values for the appropriate test is deemed to be the extreme analysis center.

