9. DETERMINATION OF SAMPLE SIZE

The following power calculations are based on the observed Week 12 results of the Phase 2 study, SGT-EBP01-09. This study was a three-arm trial including E-BPO cream, 1% and 5%, and vehicle in the treatment of rosacea. Estimates from the E-BPO cream, 5% arm were used in the power assessments. The anticipated randomization ratio is 2:1 for E-BPO cream, 5% and vehicle, respectively. The computations were performed with nQuery Advisor Version 7.0 using a two-sided test with a statistical significance value of 0.05.

A sample size of 86 in the E-BPO cream, 5% and 43 in the vehicle group has 95% power to detect a statistically significant difference in the proportion of patients who have at least a 2-grade reduction at Week 12 from Baseline in IGA and are clear or almost clear. The estimated percentages with a 2-grade reduction at Week 12 from Baseline in the IGA and clear or almost clear are 53.3% and 20.0% for the E-BPO cream and vehicle, respectively.

A sample size of 200 in the E-BPO cream, 5% and 100 in the vehicle group has 95% power to detect a statistically significant difference in inflammatory lesions. The estimated absolute change from Baseline in treatment means were -14.1 and -7.4 for E-BPO cream and vehicle, respectively, with a standard deviation (SD) of 6.70 and 17.24, respectively.

The sample sizes above will be increased to give a planned enrollment of 234 in the E-BPO cream, 5% group and 117 in the vehicle group since the Phase 3 trial is expected to enroll patients who are as a group more severe than those of the Phase 2 trial. This is a consequence of some changes in the inclusion criteria.

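### Under the SAP's own planning SDs, the 0.10 treatment-by-center test for lesion counts is not a 10% test: with no true interaction it is significant in roughly 40-70% of trials unranked and 24-43% ranked

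*SAP*

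**What the plan says.** SAP 8.1.7 sets the test up: "An analysis center by treatment interaction will be included in the primary analyses to test for parallel treatment effect at an alpha level of 0.10". For lesion counts the model is an ANCOVA with treatment, analysis center, their interaction and baseline count. It is run on raw and on ranked data, and the skewness p-value (cut at 0.01) decides which version is reported.

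The interaction p-value then has two uses.

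- **Primary model (8.7.1.1).** "If the treatment-by-analysis center interaction effect is significant at an alpha less than 0.10, then the effect will be included in the model". A term that is not significant is dropped.
- **Extreme centers (8.1.7, and step 4 of 8.7.1.1).** If the p-value is 0.10 or less, "a sensitivity analysis that excludes analysis centers with the extreme efficacy result will be performed to determine the robustness of the treatment effect". The primary analysis is then repeated without those centers.

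Section 9 gives the planning figures. Mean lesion changes are put at -14.1 (active) and -7.4 (vehicle), and the arms are listed "with a standard deviation (SD) of 6.70 and 17.24, respectively". Allocation is 2:1 and planned enrollment is 234 and 117. Section 8.1.7 sets the minimum analysis center at ten active and five vehicle patients. Neither section mentions unequal variances in the interaction test, and the number of analysis centers is not stated.

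**The concern.** An ordinary ANCOVA F test has its stated level only if the residual variance is about the same in both arms, or if the arms are balanced. Neither holds here: the arm with the larger planned SD is also the smaller one. Center-specific treatment effects therefore scatter more than the pooled residual variance predicts, even when the true effect is the same everywhere. The test reads noise in the small vehicle cells as inconsistency between centers.

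At stake is the credibility of the consistency assessment. A chance result would be reported as significant heterogeneity across centers. It would lead to a repeat analysis on a subset selected from the data, and it would add a term to a co-primary model.

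**Working it through.** **1. The plan's own figure.** Inputs from SAP section 9: difference 14.1 - 7.4 = 6.7; SDs 6.70 and 17.24; n = 200 and 100; two-sided 0.05.

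SE = sqrt(6.70²/200 + 17.24²/100) = sqrt(0.224 + 2.972) = 1.788. Power = Φ(6.7/1.788 - 1.96) = 96.3% (96.0% with a t reference), against a stated 95%. The minimum for 95% is 186/93, so 200/100 looks like a round-up. A common SD of 17.24 would give only 88.7%. The unequal SDs are therefore what the sponsor's calculation rests on.

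**2. Variance of a center effect.** For a minimum center of 10/5:

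- true variance: 6.70²/10 + 17.24²/5 = 4.49 + 59.44 = 63.9
- pooled variance: (2 × 44.89 + 297.22)/3 = 129.0
- variance assumed by the F test: 129.0 × (1/10 + 1/5) = 38.7
- ratio: 63.9/38.7 = 1.65

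Weighting the pooled variance by within-cell degrees of freedom raises the ratio slightly. With 14 centers it is (220 × 44.89 + 103 × 297.22)/323 = 125.4. The ratio is then (44.89/2 + 297.22)/(1.5 × 125.4) = 1.70.

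**3. Resulting level.** With 14 centers the 0.10 critical value on 13 and 322 df is 1.545. The chance of exceeding it is about P(F > 1.545/1.70) = P(F > 0.909) = 54%.

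**4. Simulation.** The SAP's ANCOVA was simulated with 234/117 patients, no true interaction and 1,500-2,000 trials per setting. The number of centers is an assumption. At N = 351 the 15-patient minimum caps it at 23 (351/15 = 23.4).

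| Centers | Formula, unranked | Simulated, unranked | Simulated, ranked | With skewness switch, normal errors | With skewness switch, skewed errors |
|---|---|---|---|---|---|
| 8 | 41% | 41% | 31% | 39% | not run |
| 10 | 46% | 46% | 32% | 44% | 24% |
| 14 | 54% | 53% | 35% | 50% | 27% |
| 20 | 65% | 67% | 39% | 63% | not run |
| 23 | 70% | 71% | 43% | 66% | 37% |

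The ranked column is for normal errors; with skewed errors the ranked rate is 24-36%. Pooling 28 uneven sites by the 8.1.7 rule gave a median of 14-18 centers and 54-62% unranked.

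The skewed case uses shifted gamma errors matched to Phase 2. SAP section 4 gives median reductions of 10 (vehicle) and 15 (active), against mean reductions of 7.4 and 14.1 in section 9. This implies skewness of about 0.8-0.9. The switch then selects ranks in over 99% of trials; with normal errors it does so in about 16-18%.

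**5. Dependence on the SD ratio (unranked, 14-23 centers).** SDs of 12 and 17.24 give 27-34%, 15 and 17.24 give 16-18%, and equal SDs give 10%.

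**6. Effect on the primary verdict.** Switching the model according to the interaction result changed the 0.05 verdict in about 2-4% of trials with no treatment effect. At the planned difference it changed the verdict in 0.3-1.9%. Changes went in both directions.

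**The case against.** Four points count against making much of this.

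- **The unranked rate is only one branch.** The ranked test is less affected, and the documents point to skew: Phase 2 means and medians differ, and protocol 19.4.1 had planned ranks only. A reader might infer that the test misfires in most trials. That holds only for near-normal errors and roughly a dozen or more centers. With skew like that in Phase 2 the rate is about a quarter to a third, which is still two to four times the stated level.
- **The inputs are fragile.** The SDs come from Phase 2 arms of 30-32 patients (SAP section 4) enrolled under different lesion criteria. They are raw SDs of change, used here as residual SDs. The active SD of 6.70 equals the mean difference of 6.7 and may be a slip. The center number is unknown, and multiple imputation was not modeled because no dropout rate is given. All of this stands, and it is why the result is a range. A milder imbalance of 12 against 17.24 still gives about three times the stated level.
- **Center removal is labeled a sensitivity analysis.** Section 8.1.7 itself says the exclusion is non-random and calls for post-hoc caution if the remaining subset is not significant. A reader might infer that the primary result is recomputed on selected centers. The SAP does not say that; only the added interaction term touches the primary model.
- **The agency accepted the rule.** SAP section 10 records acceptance of the approach that adds the interaction at 0.10. This is a reason to keep the rule, but the SAP does not address how the test behaves under unequal variances.

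**Conclusion.** The stated 0.10 level is wrong under the SAP's own planning figures, on both branches. Without any true interaction, expect about 40-70% unranked and 24-43% ranked for 8 to 23 centers. With the skewness switch, expect about 40-66% for normal errors and 24-37% for skewed errors. These figures assume SDs near 6.70 and 17.24 with 2:1 allocation. They fall to about 30% at 12 against 17.24 and to 10% at equal SDs.

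The damage falls mainly on the consistency report: a false finding of center heterogeneity and an extreme-center analysis that was not needed. It would be tempting to conclude that the co-primary test itself is compromised by this rule, but the figures do not support that. The model switch changes the verdict in a few percent of trials or fewer, and the effect of unequal variances on the treatment standard error is a separate matter that exists with or without the rule.

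**What to change.** In SAP 8.1.7 and 8.7.1.1, compute the interaction p-value, unranked and ranked, from a model with arm-specific residual variances (PROC MIXED with REPEATED / GROUP=treatment). Use that one p-value both for the 0.10 inclusion rule and for starting the extreme-center search, so that two interaction tests cannot disagree. In simulation this brought the level to about 7-13% on raw and ranked data; it was not checked after multiple imputation.

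Confirm against the Phase 2 report that the active SD of 6.70 is not a transcription slip, and correct section 9 if it is.

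The cost is wording in two sections and one SAS statement, before unblinding. The 0.10 inclusion rule stays, but the test behind it changes, so this small change to a procedure the agency has seen should be disclosed in SAP section 10. Keeping the main-effects ANCOVA as primary whatever the interaction shows would be simpler. That would reopen the accepted model clause, so it is optional and not part of this fix.

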8.7.1.2 Investigator Global Assessment (IGA)

The IGA will be dichotomized into “success” and “failure” with a patient considered a success for those visits if the IGA is “clear” or “almost clear”. The analysis of the dichotomized IGA will be based on a logistic regression test with factors of treatment group and analysis center.

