12.2. Inclusion Criteria

To be included in the study, patients must meet the following eligibility /inclusion criteria:

1. Patient must sign an Institutional Review Board (IRB) approved written informed consent for this study.
2. Male and female 18 years of age and older.
3. Patients must have clinical diagnosis of moderate to severe rosacea with a Baseline (IGA Score of 3 (moderate severity) or 4 (severe) on a severity scale of 0 to 4.
4. Have a minimum total of 15 and a maximum total of 70 inflammatory lesions (papules and/or pustules) including those present on the nose.
5. Have two nodules or less (nodule defined as a papule or pustule greater than 5 mm in diameter) at Baseline.
6. Patients must be willing and able to understand and comply with the requirements of the study, apply the medication as instructed, refrain from use of the following medications (during the study, return for the required treatment period visits, comply with therapy prohibitions, and are able to complete the study):
 - topical rosacea medication including: Metronizadole 0.75% to 1%, Azelaic acid, Brimonidine, Oxymetazoline, Sodium Sulfacetamide 10%, Sulfur 5%, Benzoyl Peroxide, Clindamycin, Erythromycin, Benzoyl Peroxide and Clindamycin, Sulfur lotions, retinoids, Ivermectin Cream 1%, Ivermectin lotion 0.5%, or
 - topical and systemic (oral and injectable) antibiotics known to impact rosacea e.g., tetracycline and its derivatives, erythromycin and its derivatives, doxycycline and its derivatives, minocycline and its derivatives, azithromycin and its derivatives, clarithromycin and its derivatives, metronidazole and its derivatives, sulfamethoxazole, or trimethoprim and retinoids (e.g., isotretinoin)
7. Patients must be willing to minimize or not significantly alter controllable external factors that might trigger rosacea flare-ups (such as spicy food, thermally hot foods, soups and drinks, hot environments, prolonged sun exposure, strong winds, alcoholic beverages, etc.) throughout their participation in the study.
8. Patients must be generally healthy and free from any clinically significant disease, other than rosacea, that might interfere with the study evaluations.
9. Sexually active females of child-bearing potential, excluding women who are sterilized (including Essure procedure, tubal ligation, bilateral oophorectomy or hysterectomy) or post-menopausal for at least 2 years, must use one of the following birth control options*:
 - Intrauterine device (IUD)

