13.4. Assignment of Randomization

The patient randomization schedule will be a permuted block design stratified by investigational site. Blocks will be composed of 3 treatment assignments in a ratio of 2:1 study product and vehicle, respectively. Complete blocks from the randomization schedule will be allocated to investigational sites as they randomize patients. Patients will be randomized through the IWRS and assigned a unique randomization ID indicating treatment group. The study product supplies will be packed in 4 pumps per kit and will be numbered in a scrambled randomized method. The kits will be dispensed by the IWRS according to the randomized treatment group.

The first supplied pump in each kit is marked A (e.g. number of pump within a kit is XXXXA), at Visit 4/ Week 4 the patient will return the pump and will be dispensed with the next pump which is marked B. At Visit 5/ Week 8, the patient will return the pump and will be dispensed with a pump marked C. Pump marked as D may be dispensed to patients who lost/damaged/ran-out of study product.

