19.4.2. Test of Superiority for IGA

The IGA will be dichotomized into “success” and “failure” with a patient considered a success for those visits if the Investigator’s Global Assessment is at least 2 grades less than Baseline and “Clear” or “Almost Clear”. The analysis of the dichotomized IGA will be based on a logistic regression test with factors of treatment group and analysis center.

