Encapsulated Benzoyl Peroxide Gel, 1% and 5%, and Vehicle Gel in the Treatment of Rosacea). The Phase 2 trial had two co-primary endpoints: success in Investigator Global Assessment (IGA) namely, a two-grade reduction in IGA on a scale of 0 to 4 ("clear", "almost clear", "mild", "moderate", "severe") with clear or almost clear at Week 12; and a reduction in the mean inflammatory lesion count at Week 12 (end of trial). The second co-primary endpoint was the change from Baseline in the inflammatory lesions (papules and pustules) count at end of trial. All patients were 18 years of age or older with 12 or more inflammatory lesions at enrollment. Patients were randomly divided into three groups of 30 to 32 patients each and received a once daily dose, with one group receiving S5G4T-1 (E-BPO 5%), a second group receiving a 1% concentration of E-BPO and a third control group receiving the vehicle (placebo) alone. The evaluator rated the following signs of local skin irritation on a scale of 0 to 3 ("none", "mild", "moderate", "severe") for dryness and scaling. Information on adverse events (AEs) was also collected.

Both E-BPO 1% and S5G4T-1 demonstrated statistically significant improvement in comparison to the vehicle in reducing papulopustular lesions based on the percentage change in the inflammatory lesion count from Baseline at Week 12, $p = 0.014$ and $p = 0.02$, respectively, and S5G4T-1 also demonstrated statistically significant improvement in comparison to the vehicle in achieving the IGA success co-primary endpoint ($p = 0.0013$). All three formulations were well tolerated. A few patients had moderate local application site irritation (dryness, scaling, pruritus, stinging and burning) during treatment.

A clear trend of dose response with IGA success of 20.0% for the vehicle, 37.5% for the E-BPO 1% and 53.3% for S5G4T-1 was observed. Both S5G4T-1 and E-BPO 1% significantly reduced the number of inflammatory lesions with a trend towards dose response indicated by median reduction of 10 lesions in the vehicle group compared to 12.5 and 15 in the E-BPO 1% and S5G4T-1 groups, respectively.

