8.1.4 Adjustments for Covariates

Baseline lesion count will be a covariate for the primary efficacy endpoint for lesion counts. No other covariates are planned to be used in the analyses for this study.

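### Optional, not an error: the co-primary IGA model could adjust for baseline IGA (3 vs 4), with no power gain at the planned effect and usually a small one at an assumed smaller effect

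*SAP*

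**What the plan says.** SAP 8.7.1.2 sets the model for dichotomized IGA: "The analysis of the dichotomized IGA will be based on a logistic regression test with factors of treatment group and analysis center". Protocol 19.4.2 agrees: "based on a logistic regression test with factors of treatment group and analysis center". SAP 8.1.4 names baseline lesion count as the covariate for the lesion-count endpoint and adds: "No other covariates are planned to be used in the analyses for this study".

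Other passages bear on baseline IGA:

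- **Entry.** Protocol 12.2 requires a baseline IGA of "3 (moderate severity) or 4 (severe) on a severity scale of 0 to 4".
- **Randomization.** Protocol 13.4: "The patient randomization schedule will be a permuted block design stratified by investigational site". Baseline IGA is not a stratum.
- **Imputation.** The MCMC step for IGA (SAP 8.1.5.2) includes the baseline value. The model-based imputation in SAP 8.7.2.2 does not.
- **Display.** Table 14.1.2.1 shows baseline IGA by arm, and SAP 8.1.11 plans a descriptive subgroup summary for IGA 3 vs 4.
- **Other tested endpoints.** The lesion-count models (SAP 8.7.1.1, 8.7.3) and the PAPSS models (SAP 8.7.4) each include the endpoint's own baseline.

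**The concern.** Success means IGA 0 or 1, and everyone enters at 3 or 4. The two entry grades therefore face different distances to success: at least 2 grades from grade 3, at least 3 from grade 4. A baseline variable tied this closely to the outcome is a natural adjustment factor. It is already collected, and the other tested endpoints adjust for their own baselines.

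Two things are at stake, both modest. The first is precision, and so power, on an endpoint that must succeed before any secondary claim is allowed (SAP 8.1.8). The second is chance imbalance. Because randomization does not balance severity, the arms may differ in their share of grade-4 patients, and the planned test would not account for that.

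**Working it through.** **1. The plan's own figure.** Inputs from SAP section 9: 53.3% vs 20.0%, 2:1 allocation, two-sided 0.05, 95% power. With p̄ = (0.200 + 2 × 0.533)/3 = 0.422 and d = 0.333, the vehicle arm needs

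n = [1.960 √(1.5 × 0.422 × 0.578) + 1.645 √(0.2 × 0.8 + 0.533 × 0.467/2)]² / 0.333² = 38.4.

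The continuity correction, (n/4)[1 + √(1 + 3/(n d))]², gives 42.8. That is 43 vehicle and 86 active, as the plan states.

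**2. Power at 234 and 117 with the planned rates (no center term).** Log odds ratio = ln(0.533/0.467) − ln(0.2/0.8) = 1.519. Variance = 1/(234 × 0.533 × 0.467) + 1/(117 × 0.2 × 0.8) = 0.0706, so SE = 0.266, z = 5.72 and power = Φ(5.72 − 1.96) = 99.99%. With baseline IGA added (10-30% severe, log-odds 0 to −1.4), relative efficiency is 1.000 to 1.069 and power is 99.991-99.996%. There is no usable gain.

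**3. An assumed smaller effect, 35% vs 20%.** SAP section 4 says of Phase 2: "Patients were randomly divided into three groups of 30 to 32 patients each". Counts of 16/30, 12/32 and 6/30 give the reported 53.3%, 37.5% and 20.0% and sum to the stated 92. The exact 95% interval for 16/30 is 34.3% to 71.7%, so 35% lies near its lower limit. Without the term: log odds ratio 0.767, SE 0.269, z = 2.86, power 81.5%.

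The severe share and its prognostic strength are not in the documents, so both are assumed. The model logit(success) = treatment + baseline IGA was calibrated to 35% and 20%, and its Fisher information gives the adjusted z. Gain in power points over 81.5%, by odds ratio (odds of success, grade 3 relative to grade 4):

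| Severe share | OR 1 | OR 3 | OR 4 | OR 6 |
|---|---|---|---|---|
| 10% | 0.0 | 0.5 | 0.7 | 1.0 |
| 20% | 0.0 | 1.0 | 1.5 | 2.1 |
| 30% | 0.0 | 1.5 | 2.2 | 3.2 |
| 50% | 0.0 | 2.1 | 3.2 | 5.0 |

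The extreme case examined at this effect, an odds ratio of 10 with 50% severe, gives 7.3.

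Relative efficiency, (z adjusted / z unadjusted)², is 1.00 to 1.06 for 10-30% severe and log-odds 0 to −1.4 (odds ratio 1 to about 4). The top value, 1.061, is worth 351 × (1 − 1/1.061) ≈ 20 patients.

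**4. Simulation with analysis center in both models.** 20,000 trials per scenario, blocks of 3, and an assumed 12 centers with SD 0.3 on the log-odds scale. Power without and with the term at 35% vs 20%:

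| Severe share | Log-odds for severe | Without | With |
|---|---|---|---|
| 10% | 0 | 85.3% | 85.3% |
| 30% | 0 | 85.2% | 85.1% |
| 10% | −0.9 | 85.6% | 86.0% |
| 30% | −0.9 | 85.3% | 86.1% |
| 10% | −1.4 | 85.8% | 86.3% |
| 30% | −1.4 | 85.2% | 87.1% |

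The level is higher than the 81.5% approximation, but the gains are of similar size. Under no effect (20% in both arms, 30% severe, −1.4), rejection was 5.1% without the term and 5.4% with it (SE 0.16). The planned test holds its level, and about 0.3 of the largest gain may be small-sample Wald behaviour.

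**5. Chance imbalance.** One SD of the difference in severe share is √[s(1 − s)(1/234 + 1/117)]: 3.4 points at s = 10% and 5.2 at s = 30%. In the strongest case of step 4 (30%, −1.4), success rates are 25.3% and 7.7% on vehicle and 43.2% and 15.8% on active (grade 3, grade 4). With the total number of severe patients fixed, vehicle carries 2/3 of an imbalance and active 1/3. The crude difference then shifts by 5.2 points × (2/3 × 0.176 + 1/3 × 0.274) ≈ 1.1 points. Its standard error is √(0.35 × 0.65/234 + 0.2 × 0.8/117) = 4.84 points.

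**The case against.** The case for leaving the model alone is strong. The documents state it consistently, SAP 8.1.4 makes the choice explicit, the only randomization stratum is site, and sites enter through analysis center. On the plan's own rates there is nothing to gain. Any gain needs three inputs that the documents do not supply: a smaller effect, the severe share and its prognostic strength. Imbalance would be visible in the baseline table and subgroup summary. Table 14.2.1.2 shows crude rates, which the extra term would not adjust. SAP section 10 records that a change to the primary lesion-count analysis was not accepted by the agency. That was the other co-primary, but it shows that changing a primary model can cost more than programming.

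All of this stands, and it makes the point optional. It does not remove the modest precision gain if baseline IGA is prognostic, or the ability of an adjusted test to account for imbalance.

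Three stronger readings are not supported:

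- **That the omission is an error or distorts type I error.** No design factor is left out, and simulated rejection under no effect is close to 5%.
- **That the plan itself shows severity to be prognostic.** SAP section 9 says "the Phase 3 trial is expected to enroll patients who are as a group more severe than those of the Phase 2 trial". This compares two trial populations. It does not show that IGA 3 vs 4 predicts success within this trial.
- **That about 2 points is a ceiling.** It holds only for the stated severe shares and odds ratios.

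**Conclusion.** An optional improvement, with a valid planned test. At 53.3% vs 20.0% and 234/117, power is about 99.99% either way. At an assumed 35% vs 20% the gain is:

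- zero if baseline IGA is not prognostic;
- 0 to about 2 points for 10-30% severe and an odds ratio up to about 4;
- about 3 to 5 points at an odds ratio of 6 with 30-50% severe. Gains of this size need baseline IGA to be strongly prognostic and many patients to be severe.

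No gain is claimed for Weeks 8 and 4, because the documents give no success rates for those visits. The conclusion is the same across the whole range examined. A sponsor confident in the Phase 2 effect could reasonably decline.

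**What to change.** If adopted, decide before unblinding:

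- Add baseline IGA (3 vs 4) as a factor in the Week 12 IGA logistic model, SAP 8.7.1.2.
- Carry it through 8.1.5.2 step 2, 8.1.7 (site and center interaction models and the extreme-center search), 8.7.2.2 (GEE model, model-based imputation and its analysis step) and 8.7.3 (Weeks 8 and 4, keeping the Firth fallback for sparse data).
- Amend 8.1.4 and record the change in section 10. That makes seven SAP sections.
- Update the footnotes of Tables 14.2.1.1, 14.2.1.2, 14.2.5.1 and 14.2.6.1.
- Optionally, show a standardised risk difference, or an odds ratio labelled as conditional on baseline IGA, beside the crude rates. Without this, only the p-value is adjusted.

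**Cost.** One model term and the edits above, with no new data collection. Any reported odds ratio becomes conditional on baseline IGA, and the term adds some sparsity at early visits with few successes. Because a co-primary model changes, SAP section 2 means a protocol amendment would be considered (the model also appears in the protocol Synopsis, 19.4.2, 19.4.6, 19.4.7.2 and 19.4.8.2). Agency discussion is possible.
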